*Your practice has agreed to participate in the research study entitled 'The OneFlorida Cancer Control Alliance: Implementing the 6As in Pediatric Primary Care'. The study is intended to learn about assessing adolescents' tobacco use in the clinic and improving patient-doctor communications about tobacco use. This study is supported by the Florida Department of Health James and Esther King Biomedical Research Program, with [name] serving as the Primary Investigator.*

*We are asking the Medical Director and/or Office Manager of each participating practice site to complete a survey about the overall practice structure. The brief confidential survey should take approximately 15 minutes to complete. By completing this survey, you are agreeing to participate in this study. Your responses will be analyzed and presented in aggregate. Your participation in this research study is completely voluntary.*

*You should be able to complete the survey in one sitting. Please fill out the attached paper survey and return it by U.S. mail it using the envelope provided (do not put your name on the survey or your return address on the envelope).*

*Thank you in advance for your help in this work. Please feel free to contact our study coordinator, [name], at [contact] should you have any questions about this letter or the study.*

*Sincerely,*

*[name],*

*OneFlorida Clinical Research Consortium*

*Thank you for agreeing to participate in this survey.*

*We are interested in learning more about your experiences in screening and referring children and adolescents for tobacco and other nicotine product use.*

We are also interested in learning more about the barriers you face in screening and referrals.

This questionnaire also includes items about how your practice is organized and the strategies you use when you want to implement a new intervention.

Appendix A is to be completed by each clinician participating in the study. Appendix B is to be completed by the Medical Director and there needs to be only one completed Appendix B per practice.

**Section 1: One Florida Clinician Survey (complete for each clinician participating in the study) (Add Code for practice site)**

1. What is your terminal degree or primary professional degree?
  - a. Medical degree
  - b. Nursing degree/diploma
  - c. Allied professional diploma in respiratory science/radiation technology, etc.
  - d. Other (specify)
  
2. How would you describe your primary work setting?
  - a. University or Academic Center
  - b. Hospital based non-academic center
  - c. Federally Qualified Health Center
  - d. Community Health Center
  - e. Stand-alone (non-hospital based) multi-physician practice
  - f. Stand-alone (non-hospital based) solo practice
  - g. Other (specify)
  - h. Not Applicable
  
3. What percentage of your time do you devote to patient care?
  - a. 0%
  - b. 1-24%
  - c. 25-49%
  - d. 50-74%
  - e. 75-100%
  
4. How many years have passed since completion of your most senior degree (i.e. MD, PhD, RN,etc.)?
  - a. less than 1 year
  - b. 1-5 years
  - c. 6-10 years
  - d. 11-20 years
  - e. 20+ years
  
5. Please indicate how frequently you do the following in your interactions with patients on during preventive care visits.  
(*Response options: Never, Rarely, Some of the time, Most of the time, Always*)
  - a. Ask your pediatric patients if they smoke cigarettes
  - b. Ask your pediatric patients if they use e-cigarettes
  - c. Ask your pediatric patients if they use hookah
  - d. Ask your pediatric patients about chewing tobacco, snuff or dip

- e. Ask your pediatric patients if their parents or other family members living in the home smoke cigarettes or use other tobacco/nicotine products
  - f. Ask parents/guardians accompanying your pediatric patients if they or other family members living in the home smoke cigarettes or use other tobacco/nicotine products
  - g. Advise your pediatric patients who smoke or use tobacco/nicotine products to stop
  - h. Advise parents or guardians of your pediatric patients who smoke or use tobacco/nicotine products to stop for their health and the health of their children
  - i. Advise parents or guardians of your pediatric patients that any family members residing in the home who use tobacco/nicotine products to stop for their health and the health of their children
  - j. Refer your pediatric patients to tobacco use cessation intervention programs
  - k. Refer parents or guardians of your pediatric patients to tobacco use cessation intervention programs
  - l. Actively treat children for smoking/tobacco use cessation intervention
  - m. Actively treat parents or guardians of the children for smoking/tobacco use cessation intervention
6. During follow-up appointments for children who have a history of tobacco and nicotine product use, how often do you:  
(Response options: Not applicable, Never, Rarely, Some of the time, Most of the time, Always)
- a. Ask children about tobacco or nicotine product use
  - b. Ask parents or guardians about tobacco or nicotine product use
  - c. Ask children if they have quit smoking or stopped using nicotine products
  - d. Ask parents/guardians if they have quit smoking or stopped using nicotine products
  - e. Reinforce the importance of stopping tobacco or nicotine product use to the child
  - f. Reinforce the importance of stopping tobacco or nicotine product use to the parent/guardian
7. What do you feel are barriers to providing tobacco cessation interventions in pediatric primary care?  
(Response options: Strongly agree, Agree, No opinion or neutral, Disagree, Strongly disagree)
- a. Inability to get children to quit tobacco or nicotine product use
  - b. Inability to get parents/guardians to quit tobacco or nicotine product use
  - c. Lack of time for counseling or to set up a referral
  - d. No or limited provider reimbursement
  - e. Office layout is not conducive to private conversations with the child about tobacco and nicotine products
  - f. Child resistance to cessation treatment
  - g. Parent/guardian resistance to cessation treatment
  - h. Lack of training or experience in tobacco cessation interventions
  - i. Lack of available resources or referrals for pediatric cessation interventions
  - j. Lack of available resources or referrals for parent/guardian cessation interventions
8. Please provide your opinion/judgment for the following statements.  
(Response options: Strongly agree, Agree, No opinion or Neutral, Disagree, Strongly disagree)
- a. Tobacco and nicotine product cessation should be a standard part of pediatric primary care interventions for the child
  - b. Tobacco and nicotine product cessation should be a standard part of pediatric primary care interventions for the *parents/guardians*
  - c. I have had adequate training in tobacco and nicotine product cessation interventions
  - d. Clinicians need more training in tobacco and nicotine product assessment and cessation interventions
9. Have you smoked at least 100 cigarettes or used other tobacco products in your life?

- A. Yes
- B. No
- C. Don't know

10. Do you now smoke cigarettes or use other tobacco products every day, some days, or not at all?

- A. Every day
- B. Some days
- C. Not at all
- D. Not willing to answer

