Despite national recommendations, compliance with the 6As and other PCP office-based best practices are low. The majority of pediatricians advise patients who smoke to quit (81%) but only one-third discuss cessation strategies, and less than 20% make referrals to the quitline or other cessation programs. Facilitators to carrying out the 6As and other best practices in primary care include: incorporation of cues into electronic health records (EHRs); use of short screening tools to identify those at risk for initiating tobacco use as well as current tobacco users; development of patient registries to track outcomes and to facilitate implementation of mHealth applications focused on tobacco cessation; and training of clinicians and office staff on cessation counseling.

The primary purpose of our study is to conduct a pilot, practice-based intervention focused on increasing adherence to the 6As for youth ages 11 through 17 years. We also will incorporate AAP best practice recommendations to screen and counsel parents.

Secondarily, we want to better understand the effects of the practice intervention on enhancing practice capacity to adopt and sustain new interventions in the future. The systematic uptake of evidence-based practices (EBP) into primary care is influenced by multiple organizational characteristics including practice leadership, ability to adopt new interventions (capacity for change) and sustain them (adaptive reserve); HIT availability, and clinician self-efficacy around the particular EBP. Therefore, we will measure practice characteristics including practice capacity for change, adaptive reserve, and HIT capabilities and clinician self-efficacy around the 6As at baseline and at 3 months post intervention.

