## 5. Specific Aims:

**Aim 1:** Develop and deploy an electronic short screening tool for tobacco and nicotine product use into pediatric primary care workflow in conjunction with 1) clinician and office staff training on the 6As and parent screening through the use of trained Clinical Practice Facilitators (CPFs), 2) clinician-engaged adaptations of the intervention to fit their practice workflow, and 3) support for Maintenance of Certification (MOC) to engage pediatricians in implementing the best practices.

[figure not shown]
**Aim 2:** Gather pilot data about the effectiveness of the intervention on clinician adherence to best practices and changes in practice capacity for change, adaptive reserve, and clinician self-efficacy.

**Aim 3:** Examine the congruence between documentation of the intervention in the EHR and youth report of the intervention.

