### **6.2.3 Data Collected**

A. Clinician Survey (Appendix A): Each clinician in the practice who will be participating in the study will be asked to complete a 10 minute survey about their knowledge of and current practices related to tobacco and nicotine product screening and interventions with their patients. These data will be collected at baseline and at 3 months post the intervention (9 months).

B. Practice Characteristic Data (Appendix B): The Change Process Capability Questionnaire (CPCQ) will be administered to all participating practices at the beginning and end of the study (baseline and 9 months). The CPCQ is designed to assess three domains: (1) the practices' history of change; (2) capacity for internal improvement and refinement; and (3) capacity to initiate and sustain change. Managing change is a key component necessary to adopt evidence-based best practices and the CPCQ provides valuable information about this dimension. Practices also will be asked to complete Adaptive Reserve Questionnaire (short form) at baseline and 9 months. This Survey was used in a National Institutes of Health (NIH)-funded study focused on deploying a health information technology (HIT)-enabled intervention to facilitate medical record reviews in primary care practices. The questions are designed to assess: (1) physician self-efficacy (current practices, comfort with, beliefs about, and barriers toward tobacco screening and counseling); and (2) the organizational structure available to support the implementation of new interventions such as the 6As intervention. This survey also will be administered at baseline and the end of the intervention period. The Medical Director for the practice will be asked to complete both surveys. This individual can ask for assistance from the Office/Practice Manager but most of the questions require a physician who is knowledgeable about the practice to complete the survey. Both surveys will take approximately 20 to 30 minutes to complete..

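### Change in clinician self-efficacy is an Aim 2 outcome, but the Clinician Survey shows no clinician identifier and section 6.2.5 contains no analysis of it

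*Combined protocol and SAP*

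**What the plan says.** Section 5, Aim 2, sets out to gather pilot data that include "changes in practice capacity for change, adaptive reserve, and clinician self-efficacy". Section 4 commits to measuring "clinician self-efficacy around the 6As at baseline and at 3 months post intervention". Section 6.2.3, item A, has every participating clinician complete the Clinician Survey at baseline and at 9 months, and section 6.2.4 repeats this for both arms.

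The heading of the clinician form (Appendix A, Section 1) carries the note "Add Code for practice site" and shows no other identifier. The covering letter tells respondents "do not put your name on the survey or your return address on the envelope". That letter is written to practice leadership: "We are asking the Medical Director and/or Office Manager of each participating practice site to complete a survey about the overall practice structure". The packet that it introduces nevertheless holds both Appendix A, one per clinician, and Appendix B, one per practice.

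Section 6.2.3, item B, describes physician self-efficacy in its paragraph on the practice questionnaires, and adds: "The Medical Director for the practice will be asked to complete both surveys".

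Section 6.2.5 has three parts: record-based adherence to the 6As, practice characteristics from Appendix B, and agreement between the EHR and youth report.

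**The concern.** A practice code is enough to link Appendix B, because each practice returns one. It does not link Appendix A, which every clinician in the practice returns. If the forms are used as printed, the baseline and 9-month answers become two unconnected sets of responses per practice.

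Three things are then lost. The analysis cannot adjust a clinician's follow-up score for that clinician's own baseline, although baseline adjustment is the approach that section 6.2.5 takes elsewhere. The SE for change has to be computed as if the waves were independent. A shift in the mean also cannot be separated from clinicians joining, leaving or not answering the second wave. In addition, the within-clinician correlation, which a pilot could usefully supply for a larger study, cannot be estimated.

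Separately, an outcome named in an aim has no defined score and no planned analysis, and the text assigns it to a form on which it does not appear.

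**Working it through.** **Tracing the outcome**

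- *Aim and schedule.* Sections 4 and 5 and section 6.2.3, item A, agree: clinician self-efficacy, two time points, each participating clinician.
- *Instrument.* Item B of 6.2.3 gives self-efficacy four elements: what clinicians currently do, how comfortable they are, what they believe, and what stands in the way. Appendix B as printed has two parts, on practice structure and on change process capability, and neither asks about these. Appendix A does: questions 5-6 cover current practice, question 7 barriers and question 8 opinions. Comfort has no direct item; 8c, on adequacy of training, comes nearest.
- *Identifier.* Appendix A shows a practice-site code. Section 10 (Data Plan) mentions no clinician code or key. Matching on questions 1-4 (degree, setting, share of time in patient care, years since degree) would be unreliable, because colleagues share a setting and banded answers can coincide or change.
- *Analysis.* The adherence models use three medical-record outcomes. The practice ANCOVA draws on Appendix B and lists meeting frequency, performance evaluation and planned communication. The concordance analysis uses records and youth report. None uses Appendix A.

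**Size**

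The plan gives no number of clinicians, SD, correlation or power for this outcome, so it has no figure to reproduce. What follows is illustration. Assume n clinicians answer both waves, with common SD s and within-clinician correlation r, and ignore clustering.

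The mean change is the follow-up mean minus the baseline mean, and it is the same number whether or not the forms are linked.

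- Its actual variance: 2(1-r)s²/n.
- The variance that must be used when r cannot be estimated: 2s²/n.
- Ratio of computed to actual SE: 1/sqrt(1-r).

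At r = 0.3, 1/sqrt(0.7) = 1.20. At r = 0.5, 1/sqrt(0.5) = 1.41. At r = 0.7, 1/sqrt(0.3) = 1.83.

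For the comparison of arms, take s = 1 and an assumed m = 10 clinicians per arm:

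| Analysis | SE | r = 0.3 | r = 0.5 | r = 0.7 |
|---|---|---|---|---|
| Difference in change, SE computed unlinked | sqrt(4/m) | 0.632 | 0.632 | 0.632 |
| Difference in change, linked | sqrt(4(1-r)/m) | 0.529 | 0.447 | 0.346 |
| Follow-up means only, unlinked | sqrt(2/m) | 0.447 | 0.447 | 0.447 |
| Follow-up adjusted for own baseline, linked | sqrt(2(1-r²)/m) | 0.427 | 0.387 | 0.319 |

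Rows 1 and 2 concern the same point estimate when the same clinicians respond. Rows 3 and 4 are different estimators, so that gain is real: the SE is multiplied by sqrt(1-r²), which is 0.95, 0.87 and 0.71. All these SEs are optimistic, because clinicians are clustered in four practices.

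**The case against.** The strongest reply is that the letter does not govern the clinician form. It is addressed to the Medical Director and/or Office Manager and concerns practice structure, so its no-name instruction reaches Appendix A only because that form is in the same packet. It calls the survey confidential, not anonymous, and a rule against writing a name does not forbid a pre-printed number. The note about a practice code may be an instruction to whoever builds the form. The text immediately before the letter was not available, so an identifier stated there cannot be excluded. All of this stands. It limits the claim to what the supplied text shows; it does not supply a linkage procedure, and it leaves the missing analysis untouched.

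A reader might infer that within-clinician change is the plan's stated question. It is not stated. Section 4 treats this as a secondary interest in practice capacity, and change in practice or arm means is a legitimate reading that a practice code supports.

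A reader might also take 1/(1-r), which is 2.0 at r = 0.5 and 3.3 at r = 0.7, to mean that unlinked data need that many times the clinicians for equal precision. That does not follow: with the same responders the estimated change is identical, and only its computed SE is inflated.

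Finally, if item B really places self-efficacy in the Medical Director's survey, the practice ANCOVA might be said to cover it, since its list of characteristics is introduced as examples. Appendix B as printed has no items to support that reading, and one director's answers would not measure each clinician.

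**Conclusion.** The point holds in a limited form. The supplied text names change in clinician self-efficacy as an outcome and surveys each clinician twice. It shows no clinician identifier, misplaces the construct in section 6.2.3, and plans no analysis of it. The absence of an analysis and the misplacement rest on the documents directly. The lack of linkage rests on the form as printed.

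The cost in precision is an SE for change overstated by a factor of 1.20 to 1.83 for r between 0.3 and 0.7. This assumes that the same clinicians answer both waves and ignores clustering; r is an assumption throughout. If responders differ between waves, the overstatement is smaller, but change is then confounded with who answered. The documents do not support calling the surveys impossible to link in any circumstances.

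This is a secondary outcome of a four-practice pilot and does not affect the primary outcome. It is worth correcting before baseline forms go out, because linkage cannot be recovered once unlabelled forms have come back.

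**What to change.** 1. Print a pre-assigned pseudonymous clinician number on both waves of Appendix A, with the key held separately by the study coordinator. Amend the letter to say so. Amend section 10, which now confines the use of identifiable data to the record review.
2. Correct section 6.2.3 so that clinician self-efficacy is assigned to Appendix A and not to the practice surveys.
3. Define the score from named items within questions 5-8, consistent with the definition in section 6.2.3. Questions 7-8 alone would not do: they are mostly barriers and opinions, and they omit current practice.
4. Add to section 6.2.5 an intervention-versus-control comparison of the follow-up score, adjusted for the clinician's own baseline, reported by practice and treated as descriptive given two practices per arm.
5. Report how many clinicians lack the second wave, and their baseline scores. Restricting the analysis to clinicians with both waves does not remove selective response; this shows how far it may matter.

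The work is a code list and short edits to the letter, section 6.2.3, section 6.2.5 and the Data Plan. The real cost is that responses, including questions 9-10 on the clinician's own tobacco use, become confidential rather than anonymous, which may reduce candour. The letter already promises confidentiality and aggregate reporting, and a separately held key is compatible with both.

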### 6.2.2 Sample

In Florida, only 4.3 percent of children ages 11 to 17 are current cigarette smokers. However, e-cigarette use is increasing from 5 percent of Florida high school students in 2013 to 11 percent in 2014. While the percentage of adolescents at risk to begin smoking is not known, studies have identified maternal smoking, trying tobacco, alcohol or marijuana by 8th grade, and endorsement of sensation seeking behavior as risk factors for tobacco and related product use. Children should be screened for these risks.

We will screen all youth, ages 11 through 17 years, in the practice for current tobacco use and risk behaviors associated with cigarette and nicotine product use with the goal of reaching 20 children per practice who are current tobacco users who could receive at least one or more of Steps 3 through 6 (advise, assess, assist, arrange). To achieve 20 patients per practice who reach the “advise” and “assess” stages, if the practice had the average percentage of children using e-cigarettes, approximately 218 patients would need to be screened. The number screened to reach the “advise” and “assess” stages is based on the e-cigarette use and not the traditional cigarette use.

Intervention practices will be asked to screen patients for tobacco and nicotine product use (using the anticipate and ask components of the 6As) by having youth complete a tobacco and nicotine use screening tool until the practice has identified and completed at least the “advise” and “assess” intervention on 20 tobacco/nicotine users. Parental consent and adolescent assent will be electronically obtained using ResearchActs software. In addition, practices will be asked to implement a short parental screening tool for tobacco use. The parent and child will respond to the surveys separately. After the child completes the survey s/he will be offered a \$5 electronic Amazon gift card.

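### Clinician survey question 5, items g to i, asks how often tobacco users are advised to stop but has no not-applicable answer, so a change between waves can partly reflect how many users were identified

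*Combined protocol and SAP*

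**What the plan says.** The clinician survey (section 6.2.3, item A; Appendix A) is given at baseline and at 9 months. It bears on Aim 2, and Figure 2 lists clinician changes as an outcome in both arms.

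The stem of question 5 is "Please indicate how frequently you do the following in your interactions with patients on during preventive care visits", with the scale "Response options: Never, Rarely, Some of the time, Most of the time, Always". Question 6, on follow-up of children with a history of use, has the scale "Response options: Not applicable, Never, Rarely, Some of the time, Most of the time, Always".

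Within question 5, the advise, refer and treat items are of two kinds:

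- Items g, h and i are worded about users. Item g reads "Advise your pediatric patients who smoke or use tobacco/nicotine products to stop". Item h concerns parents or guardians, though its grammar leaves open who the user is. Item i concerns household members who use.
- Items j to m are not restricted to users. Item j reads "Refer your pediatric patients to tobacco use cessation intervention programs" and item l reads "Actively treat children for smoking/tobacco use cessation intervention"; k and m are the parent counterparts.

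Under section 6.2.2, intervention practices screen youth until 20 users per practice have been advised and assessed. Control practices give usual care (section 6.2.1), which Figure 2 describes as including tobacco and nicotine screening and counseling. Section 6.2.5 takes the primary outcome from medical records and gives no score, model or missing-data rule for the clinician survey.

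**The concern.** Items g to i ask for a frequency among users. A clinician who knows of no user has no denominator and no way to say so. If that clinician marks Never, the answer cannot be told apart from that of a clinician who knows users and does not advise them. A blank is equally uninterpretable.

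The intervention changes how many clinicians are in that position. Between the two waves, intervention practices screen all youth and show the responses to the clinician at the point of care (section 6.2.3, item C). Answers to g to i could move in that arm without any change in how a known user is handled. At stake is whether a before-after difference on these items can be read as a change in advising, which is how Aim 2 would use it.

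**Working it through.** **Text comparison.** Question 5 has five response options and question 6 has six; the extra one is Not applicable. Appendix F makes a similar distinction: its questions 6 and 9 separate a no that arises because nobody uses tobacco from a plain no. The omission in question 5 is therefore out of line with the study's other instruments.

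**Illustration for item g.** The plan states no figure for question 5, so there is nothing to reproduce. The calculation below shows only how the mechanism behaves.

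Inputs from section 6.2.2:
- Cigarettes: "In Florida, only 4.3 percent of children ages 11 to 17 are current cigarette smokers", so p = 0.043.
- E-cigarettes: 11% of Florida high school students in 2014, so p = 0.11. The study also enrols younger children.

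Assumptions, not in the documents:
- Share of users known to the clinician: d = 0.3 before and 0.9 after.
- Adolescents the clinician has in mind when answering: n = 25, 50 or 100.
- Clinicians with known users keep an unchanged habit of Most of the time, scored 3 on a 0 to 4 scale.

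Probability of no known user: P0 = (1 - p × d)^n. For p = 0.043 and n = 25, P0 is (1 - 0.0129)^25 = 0.723 before and (1 - 0.0387)^25 = 0.373 after.

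If clinicians with no known user give an answer scored a, the item mean is a × P0 + 3 × (1 - P0). Its change is (a - 3) × (P0 after - P0 before). In the same example:
- Never (a = 0): -3 × (0.373 - 0.723) = +1.05.
- Always, as a statement of policy (a = 4): 1 × (0.373 - 0.723) = -0.35.
- Most of the time, from habit (a = 3): 0.
- Blank: the mean of scored answers stays at 3, but the number of answers changes.

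| p | n | P0 before | P0 after | Change if Never | Change if Always |
|---|---|---|---|---|---|
| 0.043 | 25 | 0.723 | 0.373 | +1.05 | -0.35 |
| 0.043 | 50 | 0.522 | 0.139 | +1.15 | -0.38 |
| 0.043 | 100 | 0.273 | 0.019 | +0.76 | -0.25 |
| 0.11 | 25 | 0.432 | 0.074 | +1.08 | -0.36 |
| 0.11 | 50 | 0.187 | 0.005 | +0.54 | -0.18 |
| 0.11 | 100 | 0.035 | 0.000 | +0.10 | -0.03 |

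Detection alone can move the item mean by about a point in one direction or a third of a point in the other, or not at all. The effect shrinks as volume and prevalence rise.

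**What the calculation does not cover.** Items h and i depend on parent and household use, for which the documents give no rate. Items j to m have no user denominator, so the formula does not apply to them.

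**The case against.** Several stronger readings are tempting, and the documents do not support them.

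- *Clinicians with no known users must answer Never, so the intervention arm's improvement is inflated.* Nothing requires that answer. The survey cover letter calls participation voluntary, no rule says every item must be completed, and question 5 sets no recall period, so a clinician may answer from habit or skip the item. The Background (section 4) reports that 81% of pediatricians advise patients who smoke to quit, which does not suggest that Never is the usual baseline answer to g.
- *All of g to m share the fault.* For j to m, Never is a literally correct answer when there are no users. A rise after more users are found may be a real increase in referral or treatment, which the 6As sequence intends. A not-applicable option alone would not turn these items into measures of how known users are handled.
- *The shift can occur only in the intervention arm.* Figure 2 lists screening and counseling under usual care, so control clinicians can also identify users between waves. No detection rate is given for either arm.
- *The main result is at risk.* Adherence as the primary outcome is taken from medical records, and section 6.2.5 plans no analysis of question 5.

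These objections all stand. They remove any claim about direction or size, but not the ambiguity: for g to i, Never and blank each carry two meanings that the data cannot separate. No planned analysis rule addresses this, and answers already collected at baseline could not be reclassified afterwards.

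**Conclusion.** The point holds for items g, h and i as an ambiguity in measurement. A baseline-to-9-month change on them can partly reflect how many users were identified, and the two arms can differ in this because only the intervention arm screens until users are found. Neither the direction nor the size is established. The illustrative range of about +1.15 to -0.38 points rests on assumed detection, patient volume and answering behaviour, and zero is also possible. A reader might infer a demonstrated bias in favour of the intervention; the documents do not show one. The consequence is confined to a secondary survey measure in a four-practice pilot. This is a minor point, worth acting on because the remedy is nearly free.

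**What to change.** 1. At both waves, add to items g to i an option such as: Not applicable (no such patients, parents or household members identified).
2. Decide what j to m are for. If they are meant to measure how known users are handled, reword them to refer to patients or parents identified as users and add the same option. If they are meant as overall frequency of referral and treatment, leave them unchanged and interpret them that way.
3. In section 6.2.5, state that the full response distribution for these items, including the numbers not applicable and blank, will be reported by arm and wave.
4. Treat any summary among applicable responses as descriptive only. Whether an item applies is itself changed by the intervention, so restricting the comparison to clinicians for whom it applied at both waves would condition on a post-randomisation variable. Pairing is also doubtful, because the cover letter asks for the form to be returned without a name.

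The cost is one response option, possible rewording of four items and a short reporting rule. The downside is fewer scored answers on these items.
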